- 7) **EUGLYCEMIC INSULIN CLAMP** On a separate day, subjects will be admitted to the CRC 6:45 and 8 AM for a four-hour, two-step hyperinsulinemic euglycemic insulin (20 and $80 \text{ mU/m}^2 \cdot \text{min}$) clamp with a prime-continuous infusion of $3\text{-}^3\text{H}\text{-glucose}$. The $3\text{-}^3\text{H}$ glucose prime will be $25 \mu\text{Ci} \times$ (fasting plasma glucose/100); the continuous infusion will be given at the rate of $0.40 \mu\text{Ci/min}$ for 240 minutes. Plasma samples for tritiated glucose will be obtained at 5-15 minute intervals during the 30 minutes before and throughout the insulin clamp, to quantitate rates of whole body glucose disposal and suppression of endogenous (primarily hepatic) glucose production. Continuous indirect calorimetry (Deltatrac, Sensormedics, Anaheim, CA) will be performed for 30 minutes prior to the start of the insulin clamp, and during the 210-240 period of

the insulin clamp to calculate rates of glucose and lipid oxidation Total blood loss for the procedure is up to 160 ml.

8) **Fundus Examination:** All diabetic subjects seen at the Texas Diabetes Institute have an annual ophthalmologic examination as part of their routine care. The fundus photographs will be read blindly by University of Wisconsin-Madison, Department of Ophthalmology and Visual Sciences.

Following completion of these tests, subjects will be randomized (using a table of random numbers) to receive, in open label fashion, one of the following treatment regimens:

GROUP I: Group I will be started on pioglitazone (15 mg/day) plus metformin (1000 mg/day) with the supper meal and exenatide (5 mcg s.c. bid 30 min before breakfast and supper).

If, after month one, the FPG ≥ 110 mg/dl or HbA_{1C} $\geq 6.0\%$, the exenatide dose will be increased to 10 mcg bid, pioglitazone will be increased to 30 mg/day, and metformin to 1000 mg bid.

If, after month two, the FPG ≥ 110 mg/dl or HbA_{1C} $\geq 6.0\%$, pioglitazone will be increased to 45 mg/day. Subjects who will not tolerate 5 mg bid exenatide because of GI side effects will be started on lower dose (1 mg s.c bid 30 min before breakfast and supper): and the dose will be titrated up to the maximal tolerated dose.

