- 2) Number of treatment failures in each group as defined by HbA_{1c} >6.0% and requiring the addition of rapid acting insulin with meals
- 3) Change in beta cell function
- 4) Change in whole body insulin resistance
- 5) Incidence of hypoglycemia (asymptomatic, symptomatic, serious)
- 6) Change in body weight, total body fat, and waist circumference
- 7) Change in carotid intima media thickness
- 8) Change in ankle-arm blood pressure
- 9) Change in stage of diabetic retinopathy

Change in GFR and urinary albumin secretion rate

Subjects who will complete 3-year follow-up and the repeat studies will continue to receive therapy as described above and continue in the follow-up visit every 3 months as previously described until the last subjects recruited to the study has completed 2-year follow-up. During this follow up period we will repeat the OGTT, eye photographs, DEXA and carotid ultrasound every other year (Year 3 and 6).

Washout Phase

At 6 years, all baseline studies will be repeated as stated above (OGTT, annual labs, eye photographs, ankle-arm blood pressure and carotid ultrasound). After the completion of the repeat studies, hepatic fat content and liver fibrosis will be measured with fibroscan and MRI Spectroscopy.

MRI Spectroscopy is the gold standard method to quantitate hepatic fat content. Pharmacologic therapy will be stopped if participants HbA1C is less than 7.5%. Participants with HbA1C greater than 7.5% and in the triple therapy arm, dapagliflozin (10mg/day) will be added. Participants with HbA1C greater than 7.5% in the conventional therapy arm will be switched to triple therapy. Patients will be seen every 3 months for a follow-up visit. Medical history, physical exam, body weight, blood pressure, Fasting blood sugar and HbA1c will be measured at each follow-up visit. The OGTT will be repeated at 3 months and every 6 months thereafter. Liver fat content and liver fibrosis will be measured with fibroscan annually. The 3-month follow-up visits will continue for additional 5 years, to obtain information about the long-term durability of triple therapy. Liver fat content and liver fibrosis will be measured with fibroscan and MRI annually, and the OGTT will be repeated every 2 years, and all baseline measurements will be repeated at 5 years.

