
The results of this study will provide a novel, more progressive therapeutic approach to the treatment of T2DM, based upon correction of known pathogenic abnormalities responsible for the disease.

Data Analysis and Statistical Methods

Values are presented as mean \pm SEM. Two-sided t test was used to compare mean differences between treatment arms, and the χ^2 test was used to test the significance of discrete variables. The Cox proportional hazards model was used to estimate the influence of therapy on failure to maintain the treatment goal. The model was adjusted for other confounders (namely, age, sex, BMI, disease duration, and baseline HbA1c level).

Sample size calculation:

The study was powered to detect a 0.5% (60.95 SD) HbA1c difference between the two treatment arms based on the HbA1c decrease in the PROactive study (22). We calculated that 76 patients who completed the study would be required in each arm to detect significant difference between the two groups at $\alpha = 0.05$. A detailed description of the sample size

calculation is given in the Supplementary Material.

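### Retinopathy stage is an ordered endpoint, but the plan names no test that respects the order; the listed test that fits best, chi-square, can lose power

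*Combined protocol and SAP*

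**What the plan says.** Section 6a, Secondary End Points, item 9 reads "Change in stage of diabetic retinopathy". Under Specific Methods, item 8 (Fundus Examination), "The fundus photographs will be read blindly" by an outside department. Fundus examination is scheduled at baseline and repeated at three years. Neither section states the grading scale, the number of stages or what counts as a change.

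Data Analysis and Statistical Methods names three procedures:

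- "Two-sided t test was used to compare mean differences between treatment arms".
- For categorical data, the χ² "test was used to test the significance of discrete variables".
- Third, a Cox model, whose stated use is limited to loss of the glycaemic target. Covariates, including baseline HbA1c, are listed for this model only.

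No trend test, rank test or ordinal regression appears, and no sentence links retinopathy to any of the three procedures.

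**The concern.** A disease stage has a natural order. A Pearson χ² test on a table of arm by stage returns the same p value whatever order the columns are in, and spreads its sensitivity over one fewer degrees of freedom than there are columns. A steady drift of one arm towards worse stages then counts no more than an irregular scatter of the same total size. An ordinal test puts its sensitivity into the single direction that the trial's hypothesis predicts.

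Retinopathy is a graded microvascular outcome, and the Background justifies the trial partly by microvascular benefit. The grades will exist at baseline and follow-up, so an analysis that sets their order aside discards information already paid for. The plan also leaves the coding and the test open in an open-label trial, so both could be chosen after results by arm are known.

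**Working it through.** **1. The plan's own figure.** The only sample-size figure is for HbA1c: "The study was powered to detect a 0.5% (60.95 SD) HbA1c difference between the two treatment arms" and "We calculated that 76 patients who completed the study would be required in each arm". I read the garbled 60.95 as ±0.95 and take α = 0.05, two-sided.

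n per arm = 2(z₀.₉₇₅ + z_power)² SD²/δ²

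At 90% power: 2 × (1.960 + 1.282)² × 0.95²/0.5² = 2 × 10.507 × 3.61 = 75.9, so 76. At 80% power the result is 57. The 76 therefore reproduces at 90% power, which is inferred because the text states no power. Nothing comparable exists for retinopathy, so all that follows rests on assumptions.

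**2. General cost of ignoring order.** Suppose the true effect lies wholly in the direction that the ordinal test looks at. Both statistics then have the same noncentrality λ, but the ordinal test uses 1 df and Pearson uses k − 1 df for k categories. For 80% ordinal power, λ = (1.960 + 0.842)² = 7.85. For 90%, λ = (1.960 + 1.282)² = 10.51. Pearson power is P(χ²(k − 1, λ) > 95% critical value).

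| Categories | df | Critical value | Pearson power, ordinal at 80% (loss) | Pearson power, ordinal at 90% (loss) |
|---|---|---|---|---|
| 3 | 2 | 5.991 | 70.9% (9.1) | 83.5% (6.5) |
| 4 | 3 | 7.815 | 64.5% (15.5) | 78.4% (11.6) |
| 5 | 4 | 9.488 | 59.5% (20.5) | 74.0% (16.0) |
| 6 | 5 | 11.070 | 55.5% (24.5) | 70.3% (19.7) |
| 7 | 6 | 12.592 | 52.1% (27.9) | 67.0% (23.0) |

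Losses are in percentage points. This result does not depend on sample size.

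**3. One worked scenario.** Assumptions:

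- 300 per arm: the 600 planned completers in Section 4, split equally.
- Group II: 5% better, 70% unchanged, and 13/7/3/2% worse by 1/2/3/4 steps.
- A common odds ratio of 1.5 favouring Group I.

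Group II cumulative proportions of 0.05, 0.75, 0.88, 0.95 and 0.98 become 0.073, 0.818, 0.917, 0.966 and 0.987 in Group I. Worsening is thus 25% against about 18%. Simulated power, with ranges across repeated runs:

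| Analysis | Power |
|---|---|
| Rank test (Wilcoxon) on all six categories | 60–61% |
| Pearson χ² on all six categories | 34–37% |
| Pearson χ² on better/same/worse | about 50% |
| χ² on progressed yes/no | 53–54% |
| t test on number of steps changed | 52–54% |

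The full-scale loss, about 25 points, agrees with step 2: at 60% ordinal power and six categories the formula gives 24.5. With better/same/worse coding the loss is about 11 to 12 points, with yes/no about 6 to 8, and with the t test about 7 to 8. At 76 per arm the rank test itself has only about 20% power, and the full-scale loss is about 9 to 11 points.

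**4. Range.** Over 76 or 300 per arm, odds ratios of 1.3 to 2.5 and 3 to 7 categories, the simulated loss ran from about 0 to 30 points. With 3 categories it never exceeded about 11. With an odds ratio of 2.5 and 300 per arm it was under 1 point.

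**5. Where the ranking reverses.** Take 300 per arm and better/same/worse proportions of 5/85/10% against 5/90/5%. Here χ² has 54% power and the rank test 42%, because only worsening changes and the odds are not proportional. In a simulated pattern without a one-way shift, χ² had 93% and the rank test 5%.

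**The case against.** The strongest reply is that the plan never says endpoint 9 will be tested by an unordered χ². A reader might infer that from the rule for discrete variables, but the text does not go that far. A change in steps could be compared as a mean by the t test, which keeps the order, or coded as progressed yes/no, where χ² has 1 df and no extra-df penalty. That stands: χ² on the full scale is the most natural reading of the listed rule, not a stated assignment.

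Three further inferences are tempting and are not supported.

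- **A fixed loss of 20 to 26 points.** That range needs about five or six categories and mid-range power. The documents give no scale, distribution or effect size.
- **Baseline stage goes unused.** The endpoint is a change in stage, so baseline already enters. Conditioning on it in a model is a refinement whose gain has not been quantified here.
- **Progression will be rare because proliferative disease is excluded at entry.** The exclusion removes the top baseline stage. It says nothing about how often lower stages advance.

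It is also fair that an ordinal test is not always better, as step 5 shows. The Abstract's hypothesis is directional, however (better control, and fewer complications in the long term), and a table of steps by arm would reveal a two-way pattern.

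**Conclusion.** The point holds in a limited form. The outcome is ordered, the plan names no order-respecting analysis for it, and the listed test that fits it best would ignore the order if applied to the full scale. Against a consistent one-directional shift, the cost is about 9 to 28 points of power for 3 to 7 categories when the ordinal test has 80%. It shrinks at the extremes of power and under a yes/no coding. The direction is secure for that kind of shift. The size is conditional on inputs that the documents do not supply, and an effect on both improvement and worsening could favour χ².

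This is one secondary endpoint with no stated power. The primary HbA1c comparison is untouched.

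**What to change.** In Data Analysis and Statistical Methods, name the retinopathy grading scale and assign endpoint 9 an ordinal analysis. Use either a proportional-odds model of follow-up stage with randomised arm and baseline stage as terms, or a van Elteren test stratified by baseline stage. Report a common odds ratio with its 95% CI (from the proportional-odds model, also where van Elteren supplies the test), and tabulate steps improved or worsened by arm so that departures from a one-way shift can be seen.

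The cost is wording only. The blinded grades and the baseline and follow-up fundus assessments are already in the schedule, so no visit, procedure or patient is added.

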If, at any time after achieving a HbA_{1C} $\leq 6.0\%$, the HbA_{1C} rises above 6.0% and the subject is on submaximal doses of metformin or pioglitazone or exenatide, the medication(s) will be titrated up to the maximally effective dose and the subject will not be considered a treatment failure.

If, after month six, the HbA_{1C} $\geq 6.0\%$ and the subject is on maximum doses of all triple therapy medications, the subject will be considered a treatment failure. If, after month 6, the HbA_{1C} rises to $> 6.5\%$, bedtime glargine insulin (10-20 units) will be started and titrated to a maximum of 60 units to achieve a FPG < 110 mg/dl and HbA_{1C} $< 6.0\%$. If more than 60 units of glargine insulin is required to reduce the HbA_{1C} $< 6.5\%$, regular insulin will be added to each meal and adjusted based upon the pre- and post-meal blood glucose levels. These "treatment failure" subjects will continue with all follow up visits/procedures. Throughout the titration process, downward adjustments will be allowed for the development of hypoglycemia, as defined by a blood glucose less than 60 mg/dl with (symptomatic hypoglycemia) or without (asymptomatic hypoglycemia) symptoms. Serious hypoglycemia is defined as any hypoglycemic reaction requiring assistance from a third party for recovery.

GROUP II: Group II will be started on metformin, 1000 mg with breakfast and 1000 mg with supper.

If, after month one, the FPG ≥ 110 mg/dl or HbA_{1C} $\geq 6.0\%$, glipizide (5 mg) will be added: 1-2 tablets with breakfast depending on the FPG, HbA_{1C}, and discretion of the investigator in order to avoid hypoglycemia.

If, after month two, the FPG ≥ 110 mg/dl or HbA_{1C} $\geq 6.0\%$, the glipizide dose will be increased to 4 tablets (20 mg/dl).

If, after month three, the FPG > 110 mg/dl or HbA_{1C} $> 6.0\%$, bedtime basal insulin (10-20 units) will be started and titrated up to achieve a FPG < 110 mg/dl or HbA_{1C} $< 6.0\%$

If, at any time after achieving a HbA_{1C} $< 6.0\%$, the HbA_{1C} rises above 6.0% and the subject is on submaximal doses of metformin or glipizide or glargine insulin, the medication(s) can be titrated up to the maximally effective dose and the subject will not be considered a treatment failure.

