If, after month six, the HbA_{1C} $> 6.0\%$, and the subject is on maximum doses of metformin, glipizide, and glargine insulin, the subject will be considered a treatment failure. Regular insulin will be added to each meal when the HbA_{1C} rises to $> 6.5\%$ and adjusted based upon the pre- and post-meal blood glucose levels. These "treatment failure" subjects will continue with all follow up visits/procedures.

Throughout the titration process, downward adjustments will be allowed for the development of hypoglycemia, as defined by a blood glucose less than 60 mg/dl with (symptomatic hypoglycemia) or without (asymptomatic hypoglycemia) symptoms. Serious hypoglycemia is defined as any hypoglycemic reaction requiring assistance from a third party for recovery.

Following their enrollment into the study, all T2DM participants will return to the Clinical Research Center (CRC) at the TDI for follow up visits every 3 months. Telephone calls also will be made to each participant every 6 weeks. During the telephone/CRC visits, subjects will be asked questions about interim medical history, home glucose monitoring results, and compliance with the medical regimen.

During each 3-month follow-up visit to the CRC, body weight, waist circumference (Gulick III tape measure), and blood pressure (Dynamap) will be measured. Blood will be drawn for FPG and HbA_{1c}, and pharmacological therapy will be adjusted based on the HbA_{1c}, FPG, and HBGM results (see prior algorithm). Plasma lipids and 24-hour urine albumin excretion will be measured annually or more frequently as indicated by test results. In addition to glycemic control, all subjects will receive therapy for any abnormal cardiovascular risk factors: hypercholesterolemia (goal LDL <100 mg/dl), hypertriglyceridemia (goal <150 mg/dl), hypertension (goal <130/80 monthly), albumin excretion (goal < 30 mg/day). At the end of three years, the OGTT, DEXA, fundus photography, 24 hour urine for albumin, hyperglycemic clamp, ankle-arm blood pressure, and carotid IMT will be repeated.

Primary End Point: The primary end point of the study is the difference in HbA_{1c} between Group I (triple combination therapy at time of initial diagnosis) and Group II (stepwise therapy).

Secondary End Points: The following parameters will be measured as secondary endpoints;

- 1) Number of subjects in each group with HbA_{1c} < 6.0%

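### The year-6 drug stop has no exception for treatment failures held below 7.5% on mealtime insulin, and no explicit restart level after stopping

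*Combined protocol and SAP*

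**What the plan says.** **Treatment algorithms (section 6a).**

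- Group I: if after month six HbA1c is 6.0% or more and "the subject is on maximum doses of all triple therapy medications, the subject will be considered a treatment failure". Above 6.5%, "bedtime glargine insulin (10-20 units) will be started and titrated to a maximum of 60 units". If more than 60 units would be needed to get below 6.5%, regular insulin is added at meals.
- Group II: after month three, if fasting glucose is above 110 mg/dl or HbA1c above 6.0%, "bedtime basal insulin (10-20 units) will be started and titrated up to achieve a FPG" below 110 mg/dl or HbA1c below 6.0%. If after month six HbA1c is above 6.0% "and the subject is on maximum doses of metformin, glipizide, and glargine insulin, the subject will be considered a treatment failure". Once HbA1c passes 6.5%, mealtime regular insulin follows.
- Both arms: these "subjects will continue with all follow up visits/procedures".

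**Secondary End Points, item 2 (section 6a).** Treatment failure is counted as HbA1c above 6.0% together with a need for mealtime insulin.

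**Washout Phase (section 6a).** At year 6, after the repeat studies, "Pharmacologic therapy will be stopped if participants HbA1C is less than 7.5" percent. Above 7.5% the triple-therapy arm adds dapagliflozin 10 mg/day, and "Participants with HbA1C greater than 7.5% in the conventional therapy arm will be switched to triple therapy". Visits with fasting glucose and HbA1c follow every 3 months for a further five years. Row 8 of the procedure list in section 6b keeps therapy going only above 7.5%, with dapagliflozin added.

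**Safety Precautions (section 7, item 7).** Therapy is adjusted if glucose is not adequately controlled. A participant on full-dose therapy whose HbA1c stays above 8% goes back to their own doctor.

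**The concern.** The plan identifies a group who could not reach target on maximum doses and needed mealtime insulin, and it retains them. If that insulin works, their HbA1c falls into the range where the year-6 rule withdraws treatment. A low HbA1c in such a person reflects the insulin and does not show that they can manage without drugs. The rule makes no distinction between them and a participant who is well controlled on starting therapy.

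What is at stake is the safety of these participants after year 6. A second gap makes it worse: for a person already stopped, the plan does not state the HbA1c at which treatment resumes or what is resumed. Staff would have to settle both questions case by case.

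**Working it through.** No figure in the plan bears on this point, so the check sets the rules side by side.

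**Step 1. Can a mealtime-insulin failure reach year 6 below 7.5%?** Yes. Mealtime insulin enters above 6.5% in Group II. In Group I it enters when more than 60 units of glargine would be needed to get below 6.5%. The treatment goal in both arms is below 6.0%, and failures stay in follow-up. Take a failure held at 7.0%: 6.5 < 7.0 < 7.5, so the stop applies. It applies equally at 6.0%.

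**Step 2. What does the plan then do?**

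| HbA1c at year 6 | Group I failure | Group II failure |
|---|---|---|
| Below 7.5% | Therapy stopped | Therapy stopped |
| Exactly 7.5% | Not assigned | Not assigned |
| Above 7.5% | Regimen kept, dapagliflozin added (row 8) | Switched to triple therapy; insulin not mentioned |
| Staying above 8% on full dose | Returned to own doctor | Returned to own doctor |

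The regimen that the first row stops is:

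- Group I: metformin, pioglitazone, exenatide, glargine and regular insulin (5 agents).
- Group II: metformin, glipizide, glargine and regular insulin (4 agents).

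The 8% exit does not overlap the stop range, so it protects nobody in the first row.

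**Step 3. Is there an exception elsewhere?** The Washout Phase text splits by arm only, and only above 7.5%. Row 8 has no exception. The section 7 clause on adjusting therapy acts once control has been lost and has no threshold. None of these prevents the stop.

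**Step 4. Is there a restart level?** The 7.5% branches are written for year 6. If they are read as standing rules, a stopped Group II participant who rises above 7.5% would receive triple therapy. For a stopped Group I participant, adding dapagliflozin presupposes a regimen to add it to. No explicit restart rule covers both arms.

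**Step 5. What is untouched?** The primary endpoint is the HbA1c difference between arms. The sample size (76 completers per arm) rests on a 0.5-point difference and an SD of 0.95, reading the printed 60.95 as ±0.95. It has no year-6 input. The year-6 repeat studies come before the stop.

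**The case against.** The strongest reply is that a washout means stopping drugs. The titration rules belong to the treatment period, and any washout reverses them for everyone. Monitoring continues: HbA1c every 3 months, calls every 6 weeks, and a clause allowing therapy to be adjusted. Clinicians would see a rise and treat it. Most of this stands. It limits the harm and confines the point to one phase. It does not supply an exemption, because every safeguard listed acts after control is lost.

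A reader might infer more than the documents support:

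- **That all drugs are stopped abruptly on one day.** The text is silent on order and taper; it does not order an abrupt stop.
- **That insulin is dropped at every level.** For Group I above 7.5%, row 8 maintains the regimen.
- **That the gap between thresholds (7.5 − 6.5 = 1.0 point) measures harm.** It compares rules from two phases with different purposes.
- **That HbA1c would rise by a known amount.** The background's roughly 1.5-point figures are falls on starting one drug. They do not say what follows when several are stopped years later.
- **That stopped participants would meet the 8% exit.** That exit covers people on full-dose therapy.
- **That all of the worst-controlled participants reach year 6.** Those staying above 8% on full dose leave under section 7.
- **That every participant on any insulin should be exempt.** Basal insulin is an ordinary step from month three in Group II but comes only after failure in Group I. Exempting Group I glargine users but not Group II basal-insulin users would select the off-drug groups by different rules in each arm.

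**Conclusion.** The point holds as a participant-safety gap in the washout phase. As written, the year-6 rule withdraws treatment from failures who are below 7.5% only on added mealtime insulin. It is silent on taper, and no explicit restart level covers someone already stopped. This is a stated rule with a worse safety result than a simple alternative, so it warrants an amendment.

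Its size is unknown. The documents do not give the number on mealtime insulin at year 6, the share below 7.5%, or the rise after stopping. The primary comparison, the sample size and the listed endpoints are unaffected.

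The conclusion rests on two readings: that the unqualified stop includes insulin, and that the 6-week calls set out for all enrolled participants continue after year 6, since the Washout Phase text restates only the 3-month visits.

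**What to change.** Replace the three year-6 rule sentences, and align row 8 of the procedure list, with the following:

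- **Exemption, identical in both arms.** Participants who meet the plan's secondary endpoint 2 definition (HbA1c above 6.0% and requiring mealtime insulin) do not enter the drug stop. They keep their current regimen, including insulin. At HbA1c of 7.5% or more, Group I adds dapagliflozin 10 mg/day and Group II takes triple therapy in place of glipizide.
- **Everyone else below 7.5%** stops as planned. Those at 7.5% or more follow the existing branch for their arm, which also assigns the value of exactly 7.5%.
- **Restart.** Any stopped participant in either arm restarts triple therapy at the Group I starting doses and titration if HbA1c is 7.5% or more at a 3-month visit, or if symptomatic hyperglycemia occurs between visits.
- **Reporting.** Give off-drug and post-restart HbA1c separately by randomized arm, with the number exempted in each arm.

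The cost is a short amendment and drug supply for those who continue or restart. The visits and calls already exist.

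The downside is that the off-drug group no longer contains mealtime-insulin failures. Although the rule is the same in both arms, this is selection after randomization, the numbers exempted may differ, and any off-drug comparison of the arms must say so. Group I participants on glargine alone and Group II participants on basal insulin alone still stop; the restart rule is their protection.
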